3.5.3 Handling of missing values/censoring/discontinuations

Not Applicable.

3.5.4 Supportive analyses

Not Applicable.

3.6 Analysis of the key secondary objective

Not Applicable

3.7 Analysis of secondary efficacy objective(s)

- Phase I**

The secondary objectives for the Phase I, dose escalation part of this study are:

- To determine the safety and tolerability based on NCI Common Terminology Criteria for Adverse Events (CTCAE) Version 4.03 when treated with ribociclib + everolimus + exemestane continuously in subjects with HR+, HER2 negative advanced breast cancer.
- To determine the pharmacokinetic (PK) profile of everolimus and ribociclib when dosed continuously in the triplet combination.
- To assess the preliminary anti-tumor activity of the triplet combination of ribociclib + everolimus + exemestane when combination is given continuously.

- Phase II**

The secondary objectives for the Phase II part of this trial are:

- To determine centrally assessed Progression Free Survival (PFS)
- To determine Overall Response Rate (ORR)
- To determine Overall Survival (OS)
- To determine Duration of Overall Response (DOR)
- To evaluate time to deterioration or ECOG performance status
- To determine safety and tolerability
- To determine the PK profile of ribociclib and everolimus in the triplet combination

3.7.1 Secondary end points

- **Phase I**

The secondary end points for the study are:

- Incidence and severity of adverse events (AE) and serious adverse events (SAE), clinical laboratory values, vital signs and electrocardiogram (ECGs), dose interruptions, reductions and dose intensity.
- PK parameters including, but not limited to, $AUC_{(0-4)}$, C_{trough} , C_{max} , accumulation ratio (R_{acc}).
- Progression Free Survival (PFS), Overall response rate (ORR), Disease Control Rate (DCR), Clinical benefit rate (CBR) based on the responses provided by the Investigator on locally assessed data per RECIST v1.1.

ORR, DCR and CBR will be assessed based on the responses provided by the Investigator on centrally and locally assessed data.

- **Phase II**

The secondary end points for the Phase II part of this trial, are:

- PFS
- ORR
- OS
- DOR
- Time to definitive deterioration of ECOG performance status from baseline.
- Adverse Events (AEs), serious AE (SAEs), changes in hematology and chemistry values, vital signs, dose interruptions, reductions and dose intensity.
- PK parameters including, but not limited to, $AUC_{(0-4)}$, C_{trough} , C_{max} , accumulation ratio (R_{acc}).

ORR, DOR, and PFS will be assessed based on the responses provided by the Investigator on centrally and locally assessed data.

3.7.2 Statistical hypothesis, model, and method of analysis

- **Phase I**

3.7.2.1 ORR, DCR and CBR

- ORR:

Overall response rate (ORR) defined as the proportion of patients who's best overall response is either complete response (CR) or partial response (PR) according to RECIST 1.1. ORR will be calculated based on FAS; however, patients with only non-measurable disease at baseline will be included in the numerator if they achieved a complete response. ORR will be summarized by frequency and percentage. The exact 95% two-sided confidence interval will also be provided.

When examining overall response, patients with a best overall response assessment of unknown (UNK) will not be regarded as “responders” but may be included in the denominator for ORR calculation.

Best overall response for each patient will be listed and summarized on FAS.

- DCR:

Disease control rate (DCR) is the proportion of patients with a best overall response of CR or PR or SD. DCR will be calculated based on FAS; however, patients with only non-measurable disease at baseline will be included in the numerator if they achieved a complete response. DCR will be summarized by frequency and percentage. The exact 95% two-sided confidence interval will also be provided.

When examining disease control, patients with a best overall response assessment of unknown (UNK) will not be regarded as “responders” but may be included in the denominator for DCR calculation.

- CBR:

CBR is defined as the proportion of patients with a CR, PR, SD or NCRNPD as per RECIST V1.1 by week 24. Thus, any instance of CR, PR, SD or NCRNPD in the first 24 weeks of the treatment, without having an instance of PD will be accounted for, while calculating CBR. The instances of unconfirmed CR and/or PR will also be accounted for, while calculating CBR.

CBR will be calculated based on FAS; however, patients with only non-measurable disease at baseline will be included in the numerator if they achieved a complete response. CBR will be summarized by frequency and percentage together with the 95% confidence intervals. An exact binomial confidence interval (implemented using SAS procedure FREQ with EXACT statement for one-way tables) will be calculated [Clopper & Pearson, 1934].

When examining clinical benefit, patients with a best overall response assessment of unknown (UNK) will not be regarded as “responders” but may be included in the denominator for CBR calculation.

- **Phase II**

3.7.2.2 PFS, ORR, OS and DOR

- PFS:

Progression-free survival (PFS) is defined as the time from date of treatment to the date of first documented progression or death due to any cause. For PFS, a patient who didn't have the event at the date the analysis data cut-off will be censored at the time of the last adequate assessment, prior to data cut-off. PFS will be assessed based on the responses provided by the Investigator on centrally assessed data. The PFS will be analyzed using FAS.

PFS will be analyzed using the Kaplan-Meier Product-Limit method. Estimates of the 25th, median and 75th percentile of the PFS and their 95% confidence intervals will be provided, if applicable. Additionally, above analysis will be repeated on the locally assessed tumor response. Analysis will also be performed using per protocol analysis set, as appropriate.

- ORR:

Overall response rate (ORR) defined as the proportion of patients who's best overall response is either complete response (CR) or partial response (PR) according to RECIST 1.1. ORR will be calculated based on FAS; however, patients with only non-measurable disease at baseline will be included in the numerator if they achieved a complete response. ORR will be summarized by frequency and percentage. The exact 95% two-sided confidence interval will also be provided.

When examining overall response, patients with a best overall response assessment of unknown (UNK) will not be regarded as "responders" but may be included in the denominator for ORR calculation.

Best overall response for each patient will be listed and summarized on FAS.

- OS:

Overall survival (OS) is defined as the time from date of first treatment to the date of death due to any cause. If a patient is not known to have died, survival will be censored at the last date of contact.

OS will also be summarized by Kaplan-Meier Product-Limit method based on FAS. Estimates of the 25th, median and 75th percentile of the PFS and their 95% confidence intervals will be provided, if applicable.

- DOR:

Duration of Overall Response (DOR) applies only to patients whose best overall response is CR or PR according to RECIST 1.1. The start date is the date of first documented response (CR or PR) and the end date is the date defined as first documented progression or death due to underlying cancer. In other words, the start date should be determined using the time that the response was first determined and not using the time the response was confirmed. If a patient had not had an event, duration will be censored at the date of the last adequate tumor assessment. DOR will be listed and summarized based on FAS.

DOR will also be summarized by Kaplan-Meier Product-Limit method based on FAS. Estimates of the 25th, median and 75th percentile of the DOR and their 95% confidence intervals will be provided, if applicable.

In addition of above endpoints waterfall plot and swimmer plot will also be presented. The waterfall plot displays the best percentage change from baseline in the sum of the longest diameter of all target lesions for each patient by dose cohort of phase I and by group of phase Viand swimmer plot displays patient's tumor response status with length of treatment duration.

Additionally, the concordance in best response according RECIST1.1 per central review and local evaluation will be summarized. Kappa coefficients were calculated to characterize the agreement in response assessments between local evaluation and central review (kappa = 1 implies perfect agreement).

3.7.2.3 Safety and Tolerability

Please refer to the Section [3.8](#) for Safety analysis details.

3.7.2.4 PK profile of ribociclib and everolimus

Please refer to the Section [3.9](#) for details on PK analysis for ribociclib and everolimus.

3.7.2.5 Definitive deterioration of the ECOG PS:

ECOG performance scale will be used to assess physical health of patients.

An analysis of the time to definitive deterioration of the ECOG PS by one category of the score from the date of first treatment will be performed. Baseline is the last available assessment on or before date of first treatment. Definitive deterioration is defined as an increase in ECOG PS by at least one category from the baseline score or death due to any cause. Deterioration is considered definitive if no improvements in the ECOG PS status is observed at a subsequent time of measurement during the treatment period following the time point where the deterioration is observed. (Example 1: if the score is 1 at baseline and then 1, 2, 1, 2, 3 at study days 28, 57, 83, 115, 150, respectively, then the time to definitive deterioration is 115 days, Example 2: if the score is 1 at baseline and then 1, 1, 2 at study days 28, 57, 83, respectively, with no assessment of the ECOG PS status after day 83 then the time to definitive deterioration is 83 days).

If a definitive deterioration is observed after ≥ 2 missing assessments, this event will be censored at the date of the last ECOG PS assessment prior to the deterioration. Patients that have not worsened will be censored at the date of last available assessment

Time to Definitive Deterioration (TDD) will be summarized by Kaplan-Meier Product-Limit method based on FAS. Estimates of the 25th, median and 75th percentile and their 95% confidence intervals will be provided, if applicable.

Additionally, ECOG PS data will be summarized at each scheduled assessment time point.

The following time based intervals will be used to group the ECOG PS data over time.

Table 2-6 Time window for ECOG assessment

| | Time Interval |
|----------|---|
| Baseline | Day 1 (if Day 1 data is missing then use the screening) |

| | |
|---|---|
| Cycle 2 Day 1 | Day 2 to day 42 (2 nd assessment) |
| Cycle 3 Day 1 | Day 43 to day 70 (3 rd assessment) |
| Cycle 4, 5,... until end of treatment | +/- 2 weeks centered around the planned assessment date: i.e. days 71 to 98 for Day 1 of cycle 4 (4 th assessment) days 99 to 126 for Day 1 of cycle 5 (5 th assessment) days [(k-1)*28-14; (k-1)*28+13] for Day 1 of cycle k (k+1 th assessment) |
| End of Treatment | Assessment taken at the end of treatment visit |

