7.1.8 Survival Follow-up

All patients will be follow for survival status every 24 weeks, until death, lost to follow up or withdrawal of consent, for at least 15 months after last patient enrolled into the study. Survival information can be obtained via phone, and information will be documented in the source documents and relevant eCRFs.

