7.2.2.3 Performance status

Assessment of ECOG Performance Status will be performed at screening and regularly throughout the whole study period irrespective of the time of dosing

Performance status to be performed per [Table 7-1](#) and [Table 7-3](#).

Table 7-3 ECOG performance status

Grade ECOG status
0 Fully active, able to carry on all pre-disease performance without restriction
1 Restricted in physically strenuous activity but ambulatory and able to carry out work of a light or sedentary nature e.g., light house work, office work
2 Ambulatory and capable of all self-care but unable to carry out any work activities. Up and about more than 50% of waking hours
3 Capable of only limited self-care, confined to bed or chair more than 50% of waking hours
4 Completely disabled. Cannot carry on any self-care. Totally confined to bed or chair
5 Dead

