10.5.2 Secondary objective(s)

Progression-free survival (PFS), defined as the time from date of treatment to the date of first documented progression or death due to any cause.

PFS will be analyzed using the Kaplan-Meier Product-Limit method. Patients who do not progress will be censored at the last adequate assessment. Estimates of the 25th, median and 75th percentile of the PFS and their 95% confidence intervals will be provided, if applicable.

Overall response rate (ORR) defined as the proportion of patients whose best overall response is either complete response (CR) or partial response (PR) according to RECIST 1.1. ORR will be calculated based on FAS according to the IIT principle; however, patients with only non-measurable disease at baseline will be included in the numerator if they achieved a complete response. ORR will be summarized by frequency and percentage. Disease Control Rate (DCR) in Phase I will be summarized by prior CDK 4/6 inhibitor treatment status with accompanying 95% confidence intervals.

Overall survival (OS) is defined as the time from date of first treatment to the date of death due to any cause. If a patient is not known to have died, survival will be censored at the last date of contact. OS will also be summarized by Kaplan-Meier Product-Limit method.

Duration of Overall Response (DOR) applies only to patients whose best overall response is CR or PR according to RECIST 1.1. The start date is the date of first documented response (CR or PR) and the end date is the date defined as first documented progression or death due to underlying cancer. In other words, the start date should be determined using the time that the response was first determined and not using the time the response was confirmed. If a patient had not had an event, duration will be censored at the date of the last adequate tumor assessment. DOR will be listed and summarized by treatment arm.

ECOG performance scale as described in [Table 7-3](#) will be used to assess physical health of patients. An analysis of time to definitive deterioration of the ECOG PS by one category of the score from baseline will be performed. Deterioration is considered definitive if no improvements in ECOG PS status is observed at a subsequent time of measurement during treatment period following the time point where the deterioration is observed.

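### Unless the two-missing-assessments rule covers deaths after end of treatment, time to definitive ECOG deterioration keeps future deaths at risk, drops comparable survivors, and so lowers the late Kaplan-Meier curve

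*SAP*

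**What the plan says.** - **Event.** SAP 3.7.2.5 counts an "increase in ECOG PS by at least one category from the baseline score or death due to any cause". The sentence sets no time limit on death.
- **Censoring.** "Patients that have not worsened will be censored at the date of last available assessment".
- **Missing-assessment rule.** The same section adds: "If a definitive deterioration is observed after ≥ 2 missing assessments, this event will be censored", at the last ECOG before the deterioration.
- **ECOG schedule.** The SAP's ECOG window table runs by 28-day cycle, and its last row is "Assessment taken at the end of treatment visit". In protocol Table 7-1 the performance-status row also appears to end there, though the table is broken in the text available. Protocol 7.2.2.3 reads differently: "Assessment of ECOG Performance Status will be performed at screening and regularly throughout the whole study period irrespective of the time of dosing".
- **Deaths.** Protocol 7.1.8: "All patients will be follow for survival status every 24 weeks, until death", for at least 15 months after the last patient is enrolled.
- **Protocol definition.** Protocol 10.5.2 describes worsening by one ECOG category and looks for improvement "at a subsequent time of measurement during treatment period following the time point where the deterioration is observed". It does not mention death. SAP section 5 reports no change to the protocol analyses.

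**The concern.** Kaplan-Meier estimation requires that leaving the risk set does not depend on what happens later. Take two patients with ECOG 0 throughout and end of treatment on day 120. One dies on day 480. The other is alive on day 480.

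If every death counts, the first is at risk for 480 days and has an event. The second is censored on day 120. Membership of the risk set over the intervening 480 − 120 = 360 days is then decided by the outcome. Late in follow-up the denominator holds too few survivors, each late death removes too large a share, and the curve falls too fast.

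This is a named Phase II secondary endpoint, reported with quartiles and median. As drafted, two programmers could derive different curves from the same data.

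**Working it through.** **1. The SAP's own figures.** Example 1 has baseline 1 and scores 1, 2, 1, 2, 3 on days 28, 57, 83, 115, 150. The 2 on day 57 is undone on day 83 and the 2 on day 115 is not, so the time is 115 days, as stated. Example 2 has its only worsening, on day 83, at the last assessment, so the time is 83 days, as stated. Neither example involves a death or time after treatment, so they do not settle the question.

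**2. Two readings of the missing-assessment rule.**
- Reading A: nothing is scheduled after end of treatment, so nothing is missing and every later death is an event.
- Reading B: the rule covers death, so a death more than two 28-day intervals (2 × 28 = 56 days) after the last ECOG is censored at that ECOG.

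**3. Size.** The documents give no rates for this endpoint, so these are assumptions. Treatment, ECOG worsening and post-treatment survival times are independent and exponential, with no on-treatment deaths. Accrual is uniform over 12 months (the synopsis estimate for Phase II), with cutoff 15 months after the last patient. ECOG is taken every 28 days and at end of treatment. Each set was simulated with 400,000 patients.

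The comparator E is deterioration or death over all follow-up. With a = ln2/(treatment median), b = ln2/(post-treatment survival median) and w = ln2/(ECOG median):

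E(t) = exp(−wt) × [a·exp(−bt) − b·exp(−at)] / (a − b)

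For medians 5, 18, 18 months at t = 18: a = 0.1386, b = 0.0385, exp(−bt) = 0.5, exp(−at) = 0.0825. The bracketed ratio is (0.0693 − 0.0032)/0.1001 = 0.661. Multiplying by exp(−wt) = 0.5 gives 33.0%.

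Percentage event-free (medians in months: treatment, ECOG worsening, post-treatment survival):

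| Set | A, 12 m | E, 12 m | A, 18 m | B, 18 m | E, 18 m | A − E | B − E | A, 24 m | E, 24 m | A − E |
|---|---|---|---|---|---|---|---|---|---|---|
| 5, 18, 12 | 45.1 | 45.5 | 19.3 | 37.3 | 27.4 | −8.1 | +9.9 | 3.4 | 16.0 | −12.6 |
| 5, 18, 18 | 48.8 | 50.4 | 22.6 | 40.6 | 33.0 | −10.4 | +7.6 | 4.5 | 21.3 | −16.8 |
| 5, 12, 15 | 40.1 | 38.3 | 16.6 | 27.8 | 21.6 | −5.0 | +6.2 | 2.7 | 11.9 | −9.2 |
| 7, 18, 15 | 51.0 | 51.0 | 27.1 | 42.8 | 33.4 | −6.3 | +9.4 | 8.2 | 21.3 | −13.1 |
| 5, 30, 15 | 54.1 | 58.1 | 25.8 | 52.0 | 40.4 | −14.6 | +11.6 | 5.6 | 27.4 | −21.8 |

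At 12 months A is within about 4 points of E. Medians in set order are 11.0, 11.9, 10.0, 12.3, 12.9 months under A and 10.8, 12.1, 9.1, 12.3, 14.5 under E: within about a month in four sets and 1.6 months low in the fifth. Other codings of the same sets move the ranges by a point or two, so I quote about 5 to 15 points (18 months), 8 to 22 (24 months) and, for B above E at 18 months, 4 to 12.

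**4. Sensitivity.** A wider grid of 12 scenarios at the same cutoff (treatment median 3.2 or 7.8 months, ECOG 12 or 30, post-treatment survival 9, 18 or 30) gives A − E of −10.0 to +3.0 points at 12 months and −34 to −5 at 24. With a cutoff 5.5 months after the last patient, close to a six-cycle primary report, follow-up is shorter and the distortion comes sooner: 5 to 25 points too low at 12 months.

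**The case against.** The strongest reply is that the plan already contains the limit. The SAP includes death in definitive deterioration, and the next rule censors any definitive deterioration seen after two or more missing assessments. Read that way, the death on day 480 is censored on day 120, like the survivor. The protocol statement that ECOG is assessed throughout the study supports treating later visits as missing. So a reader who infers that the SAP plainly counts death at any time goes further than the text allows.

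The opposite reading is equally open, because the SAP's windows stop at end of treatment. Where the protocol wants such a rule to cover death it says so: Table 14-7, situation C2, names progression or death. The ambiguity stands.

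A second reply is that ECOG grade 5 is death (protocol Table 7-3), so the SAP adds little. That softens the departure. But Protocol 10.5.2 does not name death as an event and judges deterioration within the treatment period, so the addition still belongs in SAP section 5.

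A third reply is that the bounded rule has its own bias. That is correct: B lies above E in every set at 18 months, and its median is further from E than A's in four of the five sets and about level in the other. The bounded rule estimates something closer to deterioration on treatment and should be labelled so.

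**Conclusion.** The point holds conditionally. If deaths after end of treatment escape the missing-assessment rule, censoring depends on the outcome. The late curve is then too low against deterioration-or-death, by about 5 to 15 points at 18 months and 8 to 22 at 24 months. With final follow-up, the five assumption sets show little effect up to 12 months and usually little on the median. All sizes rest on assumed, independent exponential rates, and an earlier cutoff brings the distortion forward.

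A reader might infer that the whole curve is pessimistic against any sensible target. It is not: in these sets the 6-month value under reading A is about 1 to 4 points too high. A reader might also want the no-improvement condition tied to one category above baseline. That condition is protocol wording and a choice between definitions, so it is not an error.

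The endpoint is descriptive. The clinical benefit rate test and the sample size are unaffected.

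**What to change.** In SAP 3.7.2.5, state that the missing-assessment rule applies to deaths after end of treatment, for example: Death counts as an event only if it occurs within two scheduled ECOG intervals (56 days) of the last ECOG assessment; later deaths are censored at that assessment. Label the output as an on-treatment deterioration estimate. In SAP section 5, replace the statement of no changes with an entry for the addition of death.

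The cost is a few sentences and minor programming. Fewer events will be counted and intervals will widen. In the 5, 18, 18 set, deaths beyond the limit occur in 29% of patients against 55% with any event under reading A, so about half of those events (29/55 = 53%) would go. The report should also say that the curve lies above an all-follow-up deterioration-or-death curve, by about 4 to 12 points at 18 months in these sets.

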3.7.2.6 Safety and Tolerability

Please refer to the Section 3.8 for Safety analysis details.

3.7.2.7 PK profile of ribociclib and everolimus

Please refer to the Section 3.9 for details on PK analysis for ribociclib and everolimus.

3.7.3 Handling of missing values/censoring/discontinuations

Missing data will not be imputed in any manner.

